7.0 COMPLIANCE TO CIP

7.1 Statements of Compliance

The study will be performed in accordance with the most current versions of the World Medical Association (WMA) Declaration of Helsinki, ISO14155 and any regional and/or national regulations and will be compliant to this International Standard and any regional and national regulations, as appropriate.

The Investigator will not start enrolling subjects or requesting informed consent from any subject prior to obtaining Ethics Committee approval and authorization from the Sponsor in writing for the study.

In case additional requirements are imposed by the Ethics Committee, those requirements will be followed, if appropriate. If any action is taken by an Ethics Committee, and regulatory requirements with respect to the study, that information will be forwarded to St. Jude Medical.

As Sponsor, St. Jude Medical has taken up general liability insurance in accordance with the requirements of the applicable local laws. Appropriate country representative will be utilized to understand the requirements for the type of insurance that will be provided for subjects, such information will be incorporated into the informed consent, as applicable.

If required, additional subject coverage or a study specific insurance will be provided by the Sponsor as well.

7.2 Adherence to the Clinical Investigation Plan

A deviation is defined as an event where the clinical investigator, site personnel, Sponsor or Sponsor representative did not conduct the clinical study according to the Clinical Investigational Plan, Ethics Committee requirements or the Investigator Agreement. The Investigator is not allowed to deviate from the CIP, except as specified under emergency circumstances.

In some cases, failure to comply with the CIP may be considered failure to protect the rights, safety and well-being of subjects, since the non-compliance exposes subjects to unreasonable risks. For example, failure to adhere to the inclusion/exclusion criteria: these criteria are specifically defined by the Sponsor to exclude subjects for whom the device is not beneficial and the use involves unreasonable risks. This may be considered failure to protect the rights, safety and well-being of the enrolled subject. Similarly, failure to perform safety assessments intended to detect adverse events may be considered failure to protect the rights, safety and well-being of the enrolled subject. Investigators should seek minimization of such risks by adhering to the CIP.

Simultaneously, in the event that adhering to the CIP might expose the subject to unreasonable risks, the Investigator is also required to protect the rights, safety and well-being of the subject by intentionally deviating from the requirements of the CIP, so that subjects are not exposed to unreasonable risks.

Ver. A

Study Name: BRADYCARE II

CIP

It is the responsibility of the Investigator to provide adequate medical care to a subject enrolled in a study.

Regulations require that the PI maintain accurate, complete, and current records, including documents showing the date of and reason for every deviation from the Clinical Investigational Plan. Relevant information for each deviation will be documented on a Deviation Form. The site will submit the form to St. Jude Medical.

Regulations require Investigators obtain approval from St. Jude Medical and the Ethics Committee [as required] before initiating changes in or deviations from the CIP, except when necessary to protect the life or physical well-being of a subject in an emergency.

Prior approval must be requested when the PI anticipates, contemplates, or makes a conscious decision to depart from the CIP, except when unforeseen circumstances are beyond the Investigator's control (e.g. a subject who fails to attend a scheduled follow-up visit, a subject is too ill to perform a CIP-required test, etc.). All deviations, including those beyond the Investigator's control, must be reported on a Deviation Form.

To obtain approval, the Principal Investigator may call or email and discuss the potential deviation with St. Jude Medical or designee prior to initiating any changes.

All deviations must be reported to appropriate regulatory authorities in specified timelines (if appropriate).

7.3 Repeated and Serious Non-Compliance

In the event of repeated non-compliance or a one-time serious non-compliance, as determined by the Sponsor, a Clinical Research Associate or clinical representative will attempt to secure compliance by one or more of the following actions:

- Visiting the Investigator
- Contacting the Investigator by telephone
- Contacting the Investigator in writing
- Retraining of the Investigator

If an Investigator is found to be repeatedly non-compliant with the signed agreement, the CIP or any other conditions of the clinical study, the Sponsor will either secure compliance or, at its sole discretion, terminate the Investigator's participation in the clinical study.

Ver. A

Study Name: BRADYCARE II

CIP

8.0 ADVERSE EVENTS

8.1 Definitions

8.1.1 Medical Device

Any instrument, apparatus, implement, machine, appliance, implant, software, material or other similar or related article:

- Intended by the manufacturer to be used, alone or in combination, for human beings for one or more of the specific purpose(s) of
 - o Diagnosis, prevention, monitoring, treatments or alleviation of disease,
 - o Diagnosis, monitoring, treatment, alleviation of, or compensation for, an injury,
 - Investigation, replacement, modification, or support of the anatomy or of a physiological process,
 - Supporting or sustaining life,
 - o Control of conception,
 - o Disinfection of medical devices and
- Which does not achieve its primary intended action in or on the human body by pharmacological, immunological or metabolic means, but which may be assisted in its intended function by such means.

8.1.2 Adverse Event (AE)

Any untoward medical occurrence, unintended disease or injury, or untoward clinical signs (including abnormal laboratory findings) in subjects, users or other persons, whether or not related to the investigational medical device under study.

This definition includes events related to the investigational medical device or the comparator. This definition includes events related to the procedures involved.

8.1.3 Serious Adverse Event (SAE)

An adverse event that led to:

- Death
- A serious deterioration in the health of the subject, that either resulted in:
 - o A life-threatening illness or injury OR
 - o A permanent impairment to a body structure or a body function OR
 - o An in-patient or prolonged hospitalization OR
 - A medical or surgical intervention to prevent life-threatening illness or injury or permanent impairment to a body structure or a body OR
 - o A malignant tumor
- Fetal distress, fetal death or a congenital abnormality or birth defect

A planned hospitalization for a pre-existing condition, or a procedure required by the CIP is not considered a serious adverse event.

8.1.4 Adverse Device Effect (ADE)

An adverse event related to the use of an investigational medical device.

Ver. A

Study Name: BRADYCARE II

CIP

This definition includes adverse events resulting from insufficient or inadequate instructions for use, deployment, implantation, installation, or operation, or any malfunction of the investigational medical device.

This definition includes any event resulting from use error or from intentional misuse of the investigational medical device.

8.1.5 Serious Adverse Device Effect (SADE)

Adverse device effect that has resulted in any of the consequences characteristic of a serious adverse event.

8.1.6 Anticipated Serious Adverse Device Effect (ASADE)

A serious adverse device effect, which by its nature, incidence, severity or outcome has been previously identified in the risk analysis report.

8.2 Procedure for Assessing, Recording and Reporting Adverse Events, Adverse Device Effects, Serious Adverse Events and Serious Adverse Device Effects:

Safety surveillance within this study and the safety reporting both performed by the Investigator, starts as soon as the subject is enrolled in this study (date of signature of the informed consent). The Investigators who agree to participate in this observational study shall be instructed to report all adverse events on enrolled patients starting from the date of implant.

The safety surveillance and the safety reporting will continue until the last follow-up visit has been performed, the subject is deceased, the subject/investigator concludes his participation into the study or the subject/investigator withdraws the subject from the study.

Adverse event data including deaths will be collected throughout the clinical study and will be reported to the Sponsor on a dedicated case report form or through the EDC system. The Investigator will record all adverse events on the appropriate case report forms.

Records relating to the subject's subsequent medical course must be maintained and submitted (as applicable) to the Sponsor until the event has subsided or, in case of permanent impairment, until the event stabilizes and the overall clinical outcome has been ascertained. Adverse events will be monitored until they are adequately resolved. The status of the subject's condition should be documented at each visit.

Reportable adverse events to the Sponsor are considered:

- Adverse Device Effects (ADEs) which include device and/or procedure related events. All ADEs will be collected from the time of device implant.
- Serious Adverse Events (whether or not the event is considered device and/or procedure related). All SAEs will be collected from the time of device implant.

All above events will be reported to the Sponsor, as soon as possible, but no later than 72 hours of first learning of the event. In case of EDC failure, notify the Sponsor via [contact].

Additional information may be requested, when required, by the Sponsor in order to support the reporting of AEs to regulatory authorities.

Study Name: BRADYCARE II

Ver. A

CIP

The Sponsor will ensure that all events are reported to the relevant authorities as per regulations.

The Investigator must notify the EC, if appropriate, in accordance with national and local laws and regulations, of the AEs reported to the Sponsor.

8.3 Device Deficiency

A Device Deficiency is defined as an inadequacy of a medical device with respect to its identity, quality, durability, reliability, safety or performance. Device deficiencies include malfunctions, use errors and inadequate labeling.

Device deficiencies are not collected in this study.

If the device deficiency involves an adverse event category as described in the protocol, the Investigator shall notify the Sponsor by completing the adverse event or death case report form as applicable and must provide the Sponsor with all necessary documentation needed.

If the device deficiency does not involve a reportable adverse event per protocol, the Investigator should notify the SJM Product Surveillance Department by emailing the information about the device deficiency to the local country office or to: [contact] or call [name] as soon as possible after becoming aware of the device deficiency. Please contact the local SJM representative to coordinate product returns as applicable.

8.4 List of Anticipated Adverse Events

The following are potential complications associated with the use of any pacing system:

- Arrhythmia
- Heart block
- Thrombosis
- Threshold elevation
- Valve damage
- Pneumothorax
- Myopotential sensing
- Vessel damage
- Air embolism
- Body rejection phenomena
- Cardiac perforation
- Cardiac tamponade
- Formation of fibrotic tissue; local tissue reaction
- Inability to interrogate or program a device because of programmer malfunction
- Infection
- Interruption of desired device function due to electrical interference

Ver. A

Study Name: BRADYCARE II

CIP

- Loss of normal desired pacing and/or sensing due to lead displacement
- Body reaction at electrode interface, or
- Lead malfunction (fracture or damage to insulation)
- Loss of normal device function due to battery failure or component malfunction
- Device migration
- Pocket erosion
- Hematoma
- Pectoral muscle stimulation
- Phrenic nerve or diaphragmatic stimulation

The following, in addition to the above, are potential complications associated with the use of rate-modulated pacing systems:

- Inappropriate, rapid pacing rates due to sensor failure or to the detection of signals other than patient activity
- Loss of activity-response due to sensor failure
- Palpitations with high-rate pacing

8.5 Subject Death

8.5.1 Procedure for Recording and Reporting Subject Death

Should a death event occur, the Investigator is required to record death information in the hospital records, immediately document the information on the Death Form and submit it to SJM. All subject deaths are to be documented and reported to the Sponsor within 72 hours after becoming aware of the event.

An Adverse Event Form should be completed in addition to the Death Form **only if there was an adverse event that led directly to the patient's death**. Otherwise, if there is no AE associated with the death, the completion of a Death Form is sufficient.

By completing the Death Form in the EDC system, the Sponsor will be automatically notified.

The subject's death means an early conclusion of the subject's participation in the study. Therefore, beside completion of a Death Form, the Investigator is required to complete the Withdrawal Form.

The Investigator must notify the Ethics Committee, if appropriate, in accordance with their reporting requirements.

9.0 DATA MANAGEMENT

Overall, the Sponsor will be responsible for the data handling.

The Sponsor and/or its affiliates will be responsible for compiling and submitting all required reports to governmental agencies.

Ver. A

Study Name: BRADYCARE II

CIP

Data will be analyzed by the Sponsor and may be transferred to the Sponsor's locations outside of Europe and/or any other worldwide regulatory authority in support of a market-approval application.

SJM respects and protects personally identifiable information that we collect or maintain. As part of our commitment, SJM is certified to the U.S. - European Union Framework and U.S. - Swiss Safe Harbor Framework Agreements regarding human resources and subject clinical trial personal information. The privacy of each subject and confidentiality of his/her information will be preserved in reports and when publishing any data. Confidentiality of data will be observed by all parties involved at all times throughout the clinical study. All data will be secured against unauthorized access.

The Principal Investigator or institution will provide direct access to source data during and after the clinical study for monitoring, audits, Ethics Committee review and regulatory authority inspections. As required, the Principal Investigator or institution will obtain permission for direct access to source documents from the subject, hospital administration and national regulatory authorities before starting the clinical study.

9.1 Data Management Plan

A detailed Data Management Plan will be established to ensure consistency of the data. This document will include procedures used for data review, database cleaning, and issuing and resolving data queries. If appropriate, the DMP may be updated throughout the study duration. All revisions will be tracked and document controlled.

CRF data will be captured in a validated electronic database management system hosted by St. Jude Medical.

Only authorized site personnel will be permitted to enter the CRF data through the electronic data capture (EDC) system deployed by SJM. An electronic audit trail will be used to track any subsequent changes of the entered data.

9.2 Document and Data Control

9.2.1 Traceability of Documents and Data

The Investigator will ensure accuracy, completeness, legibility and timeliness of the data reported to the sponsor on the CRFs and in all required reports.

9.2.2 Recording Data

Source documents will be created and maintained by the investigational site team throughout the clinical study. The data reported on the CRFs will be derived from, and be consistent with, these source documents, and any discrepancies will be explained in writing.

CRF data will be captured in a validated electronic database management Oracle Clinical system hosted by SJM.

All sites will enter data through electronic data capture (EDC). Only authorized site personnel will be permitted to enter the data through the electronic data capture (EDC) system deployed by SJM. An electronic audit trail will be used to track subsequent changes of the entered data.

Study Name: BRADYCARE II

Ver. A

CIP

10.0 MONITORING

Centralized monitoring may occur through routine internal data review. This monitoring is designed to identify missing and inconsistent data, data outliers, and potential protocol deviations that may be indicative of site non-compliance.

11.0 REGULATORY INSPECTIONS

The Investigator and/or delegate should contact St. Jude Medical immediately upon notification of a governmental agency inspection at the site. A clinical monitor or designee will assist the Investigator and/or delegate in preparing for the audit.

An Investigator who has authority to grant access will permit authorized governmental agency employees, at reasonable times and in reasonable manner, to enter and inspect any establishment where devices are held (including any establishment where devices are used or where records or results are kept).

An Investigator, or any person acting on behalf of such a person with respect to the study, will permit authorized governmental agency employees, at reasonable times and in reasonable manner, to inspect and copy all records relating to the study.

An Investigator will permit authorized governmental agency employees to inspect and copy records that identify subjects, upon notice that governmental agency has reason to suspect that adequate informed consent was not obtained, or that reports required to be submitted by the Investigator, to the Sponsor or EC have not been submitted or are incomplete, inaccurate, false or misleading.

12.0 STATISTICAL CONSIDERATIONS

12.1 Statistical Design, Hypotheses, Method and Analytical Procedures

This is a post market, prospective, non-randomized observational study.

The primary endpoint will be summarized as counts and proportion of patients who experience complications. The 95% Binomial confidence interval for the complication rate at 1 year post implant will be reported as well.

Other data will be presented using appropriate summary statistics. All continuous data will be summarized using descriptive statistics, such as the number of non-missing data, mean ± standard deviation, median and range (minimum – maximum). Categorical data will be tabulated with counts and its percentage.

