6.8 Criteria and Procedures for Subject Withdrawal or Discontinuation

Subjects must be informed about their right to withdraw from the study at any time and for any reason without sanction, penalty or loss of benefits to which the subject is otherwise entitled and withdrawal from the study will not jeopardize their future medical care or relationship with the Investigator. Subjects will be asked to specify the reason for the termination, but have the right not to answer.

The Investigator may decide to withdraw a subject from the study at any time with reasonable rationale. The subject's future care will not be influenced by a decision, voluntary or otherwise, to withdraw from the study. All reasonable efforts should be made to retain the subject in the clinical study until completion of the study.

Reasons for subject's withdrawal include, but are not limited to:

- Subject refuses to continue participating in the study
- Subject does not meet the inclusion/exclusion criteria and does not require additional follow-up for safety reasons
- Subject is deceased (Complete Death Form)
- Subject's non-compliance
- Subject's participation is terminated by the PI or Investigator, although the subject consented, since participation is no longer medically appropriate
- Subject is 'lost to follow up': Subject does not adhere to the scheduled follow up visits but has not explicitly requested to be withdrawn from the clinical study. Site personnel should at all times make all reasonable efforts to locate and communicate with the subject in order to achieve subject compliance to the scheduled follow up visits:
 - 1. A subject will be considered 'Lost to Follow Up' after a minimum of two phone calls of a physician or delegate at the investigational site to the subject or contact. These two phone calls need to be documented in the subject's hospital records.
 - 2. If these attempts are unsuccessful, a certified letter should be sent to the subject's last known address or general practitioner (GP) and a copy of this letter should be maintained in the subject's hospital records.

Note: If a subject misses one or more of the scheduled follow up visits (inclusive of the assigned visit windows), this will be considered as a missed visit requiring submission of a Deviation Form. The subject may return for subsequent visits and will not be excluded from the study.

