If a subject withdraws from the clinical study, the site will record the subject's reasons for withdrawal on a Withdrawal CRF.

When subject withdrawal from the clinical study is due to an adverse event the subject will be followed by their study doctor per standard of care outside of the study until the adverse event is resolved or the

Study Name: BRADYCARE II

Ver. A

CIP

PI determines that the subject's condition is stable. The status of the subject's condition should be documented at the time of withdrawal.

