12.2 Sample Size

The sample size calculation is based on the study design and primary objective of this study. The literature shows a complication rate of 12.2% at 1 year. Assuming the complication rate at one-year post implant is 12.2%, in order to obtain a confidence interval width of 3.1%, at least 1713 subjects will be required. Assuming a 15% attrition rate at one year, a total recruitment of 2016 subjects is needed.

Ver. A

Study Name: BRADYCARE II

CIP

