12.8 Procedures that Take into Account All the Data

All subjects who have signed a Patient Informed Consent (PIC) will be considered enrolled in the study, hence are eligible for the primary analysis. Primary analysis population will include those subjects that have signed a PIC form, and have the CIP defined pacemaker implanted.

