12.9 The Treatment of Missing, Unused or Spurious Data, Including Drop-Outs and Withdrawals

No imputation technique will be used, unless specified in the guidelines of the questionnaire data.

12.10 In Multi-Center Studies, the Minimum and Maximum Number of Subjects to be Included for each Center

This study is expected to enroll 2016 subjects in approximately 160 centers in the EMEA region and Asia-Pac region. It is desirable to have a balance of the subjects across participating centers; therefore, the maximum number of subjects to be included at each enrolling center is 200. Every effort will be made to promote recruitment; however, a low level of participation in the study could still occur, so the minimum number of subjects to be included at enrolling centers is one.

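### The primary 1-year complication rate is a crude proportion with no rule for incomplete follow-up, so taken literally it is biased down by a few tenths of a point, and by 0.9 at the extreme

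*Combined protocol and SAP*

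**What the plan says.** - **Estimator (12.1).** "The primary endpoint will be summarized as counts and proportion of patients who experience complications." A 95% binomial interval for the 1-year rate accompanies it. No time-to-event estimate is planned.
- **Population (12.8).** "Primary analysis population will include those subjects that have signed a PIC form, and have the CIP defined pacemaker implanted." No minimum follow-up is required.
- **End of event collection (8.2).** Safety surveillance runs until the last visit, death, or the point at which "the subject/investigator concludes his participation into the study or the subject/investigator withdraws the subject from the study." Later complications in leavers are not captured.
- **Missing data (12.9).** "No imputation technique will be used, unless specified in the guidelines of the questionnaire data." This is the whole provision for drop-outs and withdrawals.
- **Sample size (12.2).** 1713 subjects give a 3.1-point interval at a rate of 12.2%. Then: "Assuming a 15% attrition rate at one year, a total recruitment of 2016 subjects is needed."
- **Withdrawal (6.8).** Death is listed among the reasons for withdrawal. Withdrawal because of a complication is also foreseen: "When subject withdrawal from the clinical study is due to an adverse event the subject will be followed by their study doctor" under standard care outside the study.
- **Final visit (6.4).** It may take place two months either side of month 12.

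**The concern.** A 1-year proportion needs a known 1-year status for everyone in its denominator. Here the denominator is everyone, while status is unknown for those who leave early without an event. Adding them to the denominator with nothing in the numerator treats unobserved time as complication-free. The error runs one way, downward, and the binomial interval is then centred on the wrong value.

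Deaths without a prior complication are different. They are properly non-events for a 1-year cumulative incidence, so only withdrawal and loss cause the bias. Subjects whose final visit falls before day 365 add a smaller shortfall of the same kind.

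The rate is the study's only primary result, and the study was sized solely for its precision.

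**Working it through.** **1. The plan's own figure.** Inputs from 12.2: p = 0.122, full width 0.031, attrition A = 0.15.

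n = 1.96² × 0.122 × 0.878 / 0.0155² = 1712.7, so 1713. Then 1713 / 0.85 = 2015.3, so 2016. Both figures reproduce. The planned half-width is 1.55 points. With all 2016 subjects in the denominator the binomial full width is 2.86 points.

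**2. Bias on the literal reading.** Let F(t) be the cumulative complication rate at month t, with F(12) = p, U the time of leaving, and d the share of attrition that is death. If leaving is unrelated to risk:

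bias = −A × (1 − d) × (p − mean F(U))

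The documents do not give F, U or d. They are assumed, and the range is shown. The front-loaded patterns place a stated share of the year's complications evenly in month 1 and the rest evenly over months 2 to 12.

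Worked case (constant hazard, U even over months 0 to 12, d = 0): mean F(U) = 6.23%, so the bias is −0.15 × (12.2 − 6.23) = −0.90 points and the expected reported rate is about 11.3%.

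| Bias, points | Constant hazard | 50% in month 1 | 70% in month 1 | 90% in month 1 |
|---|---|---|---|---|
| Loss over months 0–12, no deaths | −0.90 | −0.53 | −0.35 | −0.17 |
| Loss over months 0–12, one third deaths | −0.60 | −0.36 | −0.23 | −0.11 |
| Loss over months 1–12, no deaths | −0.82 | −0.46 | −0.27 | −0.09 |
| Loss over months 1–12, one third deaths | −0.55 | −0.30 | −0.18 | −0.06 |

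**3. Visit window.** Suppose final visits are spread evenly over months 10 to 14, and complications count only if they occur by day 365 and before the visit. Half the completers are then seen early, by one month on average. The shortfall among completers is 0.48, 0.28, 0.17 and 0.06 points for the four timing patterns. Completers are 85% of the 12.2 planning population, so the crude all-subject rate loses 0.85 times this: 0.41, 0.24, 0.14 and 0.05. If events after day 365 were counted instead, late visits would offset early ones almost exactly at constant hazard. The plan does not say which applies.

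**4. Completers only.** This reading has the full window shortfall from step 3. It also loses complications that lead to withdrawal. If a share w of subjects with a complication leave because of it, and no one else's leaving depends on risk, the bias is p(1 − w)/(1 − pw) − p, which is −0.5 points at w = 5% and −1.1 at w = 10%. Both values of w are assumptions.

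**5. Precision of a censored estimate.** Greenwood variance, n = 2016, constant hazard, no deaths, 15% lost:

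| Loss | Final visits | Full 95% width, points |
|---|---|---|
| Even over the year | none early | 2.98 |
| Even over the year | even over months 10–14 | 3.08 |
| Even over the year | even over months 10–13 | 3.15 |
| Half at month 1, half at month 6 | even over months 10–14 | 3.14 |
| All at month 1 | even over months 10–14 | 3.19 |

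**The case against.** **Complications cluster near implant, and attrition may be low.** This has force. Section 8.4 lists many implant-related events, such as pneumothorax, perforation and hematoma. Section 6.7 expects no more than normal attrition and promises close monitoring of follow-up, and 6.8 requires two calls and a letter before a subject is declared lost. The −0.90 is therefore an extreme case, and a few tenths of a point is more plausible. The missing rule remains.

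**The literal reading is not forced.** Scoring an unobserved subject as complication-free is arguably an imputation, which 12.9 bars. That is fair. The defect is an unspecified rule, but the only population the plan defines is the one that produces the downward bias.

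**A reader might infer that 12.2 and 12.8 contradict each other on the denominator.** The documents do not support that. The step from 1713 to 2016 is a planning allowance for lost information. It sits uneasily with 12.8 but defines no analysis set.

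**A reader might also set other denominators against the literal one,** for example all recorded events over completers plus leavers with an event, and infer a spread wider than the planned half-width. No section proposes such a denominator, so that spread is not evidence against this plan.

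**A one-sentence denominator rule with a sensitivity analysis would be enough for a descriptive study.** It would remove the ambiguity. It would not remove the bias, because both the all-subject and the completers-only proportions fall short when follow-up is incomplete.

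**Conclusion.** The concern holds as a gap with a modest, one-directional consequence. The stated estimator applied to the stated population understates the 1-year rate by about 0.1 to 0.9 points with even loss over the year, or 0.06 to 0.55 with loss over months 1 to 12 and one third of attrition by death. Early final visits can add up to about 0.5 points. The top of each range needs a constant hazard and the bottom needs about 90% of complications in month 1. All of it rests on the planning values of 12.2% and 15% and on leaving being unrelated to risk.

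Restricting to completers is not a safe alternative, because it shares the window shortfall and drops complications that cause withdrawal. Section 12.3 sets no pass/fail criterion, so what is at stake is a somewhat low rate with a miscentred interval. It should be fixed before analysis; it does not threaten a decision.

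**What to change.** In 12.1, make the primary estimate the cumulative incidence of first complication at day 365 from implant, by the Aalen-Johansen method, with its 95% interval. Specify that:

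- death without a prior complication is a competing event, and a fatal complication is an event;
- withdrawals, losses and final visits before day 365 are censored at last contact;
- events after day 365 are not counted.

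Keep the crude count and proportion as supportive, with the denominator stated. Align 12.8 and 12.9 so that all consented and implanted subjects enter and those with incomplete follow-up contribute until censoring.

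The cost is analysis wording and standard software, with no extra visits. Three limits should be acknowledged. The method assumes censoring is non-informative, which withdrawal after an adverse event may strain. It needs dates of event, death, withdrawal and last contact, and the case report forms are under separate cover, so these fields must be confirmed. The full interval width may exceed the planned 3.1 points by up to about 0.1 if loss is early or final visits fall early in the window.
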